Safety events of interest on a sponsor study drug that may require expedited reporting and/or safety evaluation include, but are not limited to:

- Overdose of a sponsor study drug
- Suspected abuse/misuse of a sponsor study drug
- Inadvertent or accidental exposure to a sponsor study drug

• Medication error involving a sponsor product (with or without subject/patient exposure to the sponsor study drug, eg, name confusion)

Special reporting situations will be recorded in the CRF. Any special reporting situation that meets the criteria of a serious adverse event will be recorded on the serious adverse event

page of the CRF.

Procedures

All Adverse Events

All adverse events and special reporting situations, whether serious or non-serious, will be reported from the time a signed and dated ICF is obtained until completion of the subject's last study-related procedure (which may include contact for follow-up of safety). Serious adverse events, including those spontaneously reported to the investigator within 30 days after the last dose of study drug, will be reported.

All events that meet the definition of a serious adverse event will be reported as serious adverse events, regardless of whether they are protocol-specific assessments.

All adverse events, regardless of seriousness, severity, or presumed relationship to study drug, will be recorded using medical terminology in the source document and the CRF. Whenever possible, diagnoses will be given when signs and symptoms are due to a common etiology (eg, cough, runny nose, sneezing, sore throat, and head congestion will be reported as "upper respiratory infection"). Study investigators will record in the CRF their opinion concerning the relationship of the adverse event to study therapy. All measures required for adverse event management will be recorded in the source document.

The sponsor assumes responsibility for appropriate reporting of adverse events to the regulatory authorities. The sponsor will also report to Janssen Scientific Affairs, LLC all serious adverse events that are unlisted (unexpected) and associated with the use of the study drug. The sponsor will report these events to the appropriate Independent Ethics Committee/Institutional Review Board (IEC/IRB) that approved the protocol unless otherwise required and documented by the IEC/IRB.

Serious Adverse Events

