All serious adverse events occurring during the study must be reported to Janssen Scientific Affairs, LLC by study-site personnel within 24 hours of their knowledge of the event.

All serious adverse events that have not resolved by the end of the study, or that have not resolved upon discontinuation of the subject's participation in the study, must be followed until any of the following occurs:

- The event resolves
- The event stabilizes
- The event returns to baseline, if a baseline value/status is available

• The event can be attributed to agents other than the study drug or to factors unrelated to study conduct

• It becomes unlikely that any additional information can be obtained (subject or health care practitioner refusal to provide additional information, lost to follow-up after demonstration of due diligence with follow-up efforts)

Suspected transmission of an infectious agent by a medicinal product will be reported as a serious adverse event. Any event requiring hospitalization (or prolongation of hospitalization) that occurs during the course of a subject's participation in a study must be reported as a serious adverse event, except hospitalizations for the following:

• Hospitalizations not intended to treat an acute illness or adverse event (eg, social reasons such as pending placement in long-term care facility)

• Surgery or procedure planned before entry into the study (must be documented in the CRF). Note: Hospitalizations that were planned before the signing of the ICF, and where the underlying condition for which the hospitalization was planned has not worsened, will not be considered serious adverse events. Any adverse event that results in a prolongation of the originally planned hospitalization is to be reported as a new serious adverse event.

Disease progression should not be recorded as an adverse event or serious adverse event term; instead, signs and symptoms of clinical sequelae resulting from disease progression/lack of efficacy will be reported if they fulfill the serious adverse event definition.

Adverse Events of Interest

Specific adverse events or groups of adverse events will be followed as part of standard safety monitoring activities. These events will be reported to Janssen Scientific Affairs, LLC within 24 hours of awareness irrespective of seriousness (ie, serious and nonserious adverse events) following the procedure described above for serious adverse events and will require enhanced data collection.

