For Women: Vaginal yeast infections and vaginal itching: You may have symptoms such as vaginal itching, burning, irritation, odor or discharge. This side effect may occur in slightly more than 1 in 10 women on canagliflozin.

For Men: Yeast infection at the head of the penis - You may have symptoms such as penile itching, irritation, burning, swelling, foul smelling discharge or pain. In 0.3% of men who are not circumcised, this could lead to swelling of the foreskin, and require circumcision. The side effect of yeast infection may occur in up to 1 in 20 men on canagliflozin.

Increased urination and thirst – Symptoms might include feeling thirsty, having a dry tongue, urinating more frequently or in larger amounts, an urgent need to urinate or more frequent urination at night. These side effects may occur in up to 1 in 20 people taking canagliflozin.

Urinary tract infections – Symptoms of urinary tract infections may include burning with urination, discomfort in passing urine, or fever. This side effect may occur in up to 1 in 20 people on canagliflozin.

Allergic reaction including rash or hives – These events can occur shortly after starting canagliflozin, are generally not serious or associated with other serious symptoms, such as breathing problems. This side effect may occur in up to 1 in 20 people on canagliflozin.

Less Common

Constipation – The side effect of constipation may occur in slightly more than 1 in 50 people on canagliflozin.

Nausea - The side effect of nausea (stomach queasy) may occur in slightly more than 1 in 50 people on canagliflozin.

Bone fractures may occur in up to 1 in 50 people per year on canagliflozin.

- Laboratory changes that have been observed in clinical studies with canagliflozin
 - Increase in the LDL, or "bad", cholesterol.
 - Increase in serum potassium, phosphate and/or hemoglobin; decreases in serum urate can also occur. These changes are generally not serious and not associated with serious symptoms.
 - A change in lab tests associated with kidney function might occur. These changes have generally been temporary and may relate to hydration status. During the study, we regularly monitor kidney function.
 - There may be side effects with the use of canagliflozin that are not yet known.

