Side effects in patients not involved in clinical studies who have been prescribed canagliflozin to treat their diabetes include those below. It is difficult to know specifically how often these side effects occur or always be certain if they are more likely to occur as a result of canagliflozin because these were not reported in the manner similar to data collection in a clinical study.

- Serious allergic reactions, including those with the symptoms of swelling of the face, throat, and/or tongue or breathing problems.
- Changes in lab tests associated with kidney function. Cases of severe decreases in kidney function have been reported more commonly in patients who were dehydrated.
- **Diabetic ketoacidosis** The blood may show increased levels of blood acids called ketones. Sometimes this can occur even if blood sugar levels are not very high (e.g., less than 250 mg/dL [13.9 mmol/L]). Symptoms may include difficulty breathing, nausea, vomiting, abdominal pain, confusion, fruity-smelling breath, and unusual fatigue or sleepiness. This side effect may occur in up 1 in 1000 people with Type 2 diabetes.

0

Risks Associated with Blood Draw: The risks and discomforts of blood drawing from a vein include the possibility of pain or bruising at the site of the blood draw, occasional feeling of lightheadedness, and rarely, infection at the site of the blood draw.

Risks Associated with Indirect calorimetry: Subjects may feel a sense of suffocation when they are laying underneath the large plastic dome.

Risks Associated with DXA scan: This research study involves exposure to radiation from body composition scans. This radiation exposure is **not** necessary for medical care and is for research purposes only. This is in addition to the radiation exposure that you will receive as part of standard care. Using the standard way of describing radiation exposure, from participating in this study subjects will receive a total of 0.04 mSv.

For comparison, the average person in the United States receives a radiation exposure of 3 mSv per year from natural background sources, such as from the sun, outer space, and from radioactive materials that are found naturally in the earth's air and soil. The dose that subjects will receive from participation in this research study is about the same amount that he/she would normally receive in about one week from these natural sources.

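### The clause on symptoms of disease progression or lack of efficacy can be read to exempt nonserious diabetes symptoms, in conflict with the rule that all adverse events are recorded

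*Combined protocol and SAP*

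**What the plan says.** Section B3.A sets the general rule under Procedures, All Adverse Events: "All adverse events and special reporting situations, whether serious or non-serious, will be reported", from consent to the last study procedure. It adds that events, "regardless of seriousness, severity, or presumed relationship to study drug, will be recorded using medical terminology in the source document and the CRF". Attribution is a separate item: "Study investigators will record in the CRF their opinion concerning the relationship of the adverse event to study therapy". No exception is stated there.

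A little further on, under Serious Adverse Events, the same section says: "Disease progression should not be recorded as an adverse event or serious adverse event term". The sentence then turns to what is to be done instead: "signs and symptoms of clinical sequelae resulting from disease progression/lack of efficacy will be reported if they fulfill the serious adverse event definition". The protocol does not say what progression or lack of efficacy means in type 2 diabetes.

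Section B5 describes a listed canagliflozin effect that includes "feeling thirsty, having a dry tongue, urinating more frequently or in larger amounts", with a frequency of up to 1 in 20. No placebo frequency is given.

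**The concern.** The general rule makes recording independent of seriousness and of cause. The later clause, taken at its word, brings both back: once a symptom is put down to the disease or to a failure of treatment, the only route to reporting that it names is seriousness.

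This matters here because the disease and the drug can produce the same complaint. Subjects enter with A1C above 6% and below 9%, the protocol aims for a majority on lifestyle treatment alone (sections B3.B and B3.C), and half receive placebo. Thirst and frequent urination may reflect uncontrolled glucose or may be the drug effect listed in section B5. Two coordinators who both follow the text could treat the same nonserious complaint differently, one entering it and the other leaving it out as lack of efficacy. What is at stake is the completeness of the safety record for a known drug effect in a small trial. Events never entered may not be recoverable later.

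**Working it through.** The documents give no figure on this point, so there is none to reproduce. The check is a comparison of the two rules, followed by arithmetic on scale.

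**Step 1: the two rules side by side.**

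| Complaint and attribution | All Adverse Events rule | Progression clause, literal reading | Progression clause, read as governing serious events only |
|---|---|---|---|
| Nonserious thirst, put down to the drug | Recorded | Clause does not apply; recorded | Recorded |
| Nonserious thirst, put down to diabetes or lack of efficacy | Recorded | Not reported | Recorded, not handled as a serious event |
| Serious symptom, put down to diabetes | Recorded | Reported | Reported |

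Only the second row differs between readings. That row is the conflict, and the text does not say which reading applies.

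**Step 2: how many subjects could be involved.** Inputs: the ceiling r = 1/20 = 0.05 for thirst and urination on canagliflozin (section B5); n per arm is 42/2 = 21 from the 42 randomized 1:1 in section B3.A, or 50/2 = 25 from the approximately 50 enrolled in section B3.B.

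- Expected canagliflozin subjects with the event, n × r: 21 × 0.05 = 1.05; 25 × 0.05 = 1.25.
- Chance that no canagliflozin subject has it, (1 − r)^n: 0.95^21 = 0.34; 0.95^25 = 0.28.

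**Step 3: how many could go unrecorded.** Let q be the share of these events put down to diabetes and left out under the literal reading. Expected number unrecorded in an arm = n × r × q. The documents give neither q nor a placebo rate. As assumptions, take q from 0 to 100%, equal in both arms, and a placebo rate from 0 to 5%, with 21 per arm.

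| q | Unrecorded, canagliflozin | Unrecorded, placebo |
|---|---|---|
| 0% | 0 | 0 |
| 50% | 21 × 0.05 × 0.5 = 0.53 | 0 to 0.53 |
| 100% | 21 × 0.05 × 1 = 1.05 | 0 to 1.05 |

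The difference between arms in unrecorded events runs from 0 to about 1, and it depends wholly on assumed values. While q is the same in both arms and below 100%, the ratio of recorded events between arms does not change. If q differs by arm, the difference can go either way.

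**The case against.** **The clause may not exempt anything.** It stands under Serious Adverse Events, after rules on 24-hour reporting, follow-up and hospitalization. It can be read as governing serious-event reporting alone, which would leave the general recording rule whole. It does not contain the word *only*, and it never says that nonserious symptoms go unrecorded. A reader might infer that such symptoms are definitely dropped; the documents do not support that. The reply is that the heading does not fully confine the sentence. Its first half names adverse event terms as well as serious ones, and the All Adverse Events text itself uses *reported* for nonserious events. The ambiguity stands; the certainty does not.

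**The trial is double-blind.** A reader might infer that placebo symptoms would be lost while identical symptoms on canagliflozin are kept, so that the arms are unevenly affected or the comparison even reverses. With 25 per arm and an assumed placebo rate of 10%, 1.25 versus 2.5 subjects would become 1.25 versus 0. That requires every placebo event and no canagliflozin event to be put down to diabetes, and a placebo rate that the documents do not give. With a common share of 50%, the same numbers become 0.63 versus 1.25, with no reversal. Blinding does not guarantee neutral attribution: blood sugar logs are reviewed together with adverse effects at weeks 2 to 12, urine glucose is collected, and the protocol does not say that either is withheld from the assessor. Uneven loss is therefore possible, but the documents show neither that it would occur nor its direction.

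**Kidney function.** Section B5 lists "Changes in lab tests associated with kidney function" among reported side effects, and a reader might infer that modest declines would be written off as diabetic progression. This is strained. The clause concerns signs and symptoms of clinical sequelae, which a modest laboratory change is not obviously. Entry requires GFR above 60, treatment lasts 18 weeks, and section B5 says kidney function is monitored. Nothing classes such changes as progression.

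**No safety comparison is planned.** Section B3.B describes no adverse-event analysis, and the weight, metabolic and other efficacy endpoints are unaffected. This is correct and limits the consequence to the completeness of the safety record.

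**Conclusion.** The concern holds as a conflict of wording with a practical consequence. The clause can be read to exempt nonserious symptoms attributed to diabetes, against a general rule that allows no such exception, and its two exempting terms are undefined for this disease. Thirst and frequent urination are the clearest case, because they are a listed drug effect and also possible signs of poor glucose control.

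The scale is about one canagliflozin subject at the stated ceiling (1.05 to 1.25, depending on which enrollment figure is used). That is small in absolute terms, but with so few events expected, one unrecorded event could change a descriptive safety table. The conflict itself rests on no assumption. The number unrecorded rests entirely on an unknown attribution share and an unknown placebo rate, so its size, its direction and any imbalance between arms cannot be established from the documents.

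The wording should be corrected, but it does not threaten the primary result.

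**What to change.** Reconcile the two parts of section B3.A. Keep the bar on disease progression as an event term, which does no harm; deleting the whole sentence would remove it needlessly. Amend the second half to say that:

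- the underlying signs and symptoms, where new or worse than baseline, are recorded in the CRF under the All Adverse Events rule whether or not they are serious;
- the investigator's causality opinion goes in its existing separate field and does not decide whether the event is entered;
- expedited serious-event reporting applies when the serious definition is met.

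The cost is a change to one sentence and a few more nonserious CRF entries. Treatment, visits and sample size do not change.

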This is a randomized, double-blind, placebo-controlled parallel design study in which 42 subjects will be randomized (1:1) to treatment with canagliflozin 300mg or placebo once daily for 18 weeks. The study will include 7 outpatient visits which will take place in the Harvard Catalyst Clinical Research Center at BIDMC. The funding source for this study is Janssen Scientific Affairs, LLC; Janssen Scientific Affairs, LLC is also providing canagliflozin for this study.

Our primary endpoint is change in body weight. Secondary endpoints are change in resting metabolic rate measured using indirect calorimetry, change in body composition using DXA scans changes in serum markers of metabolism and inflammation, and change in hunger and satiety using visual analog scales. We will also analyze change in caloric intake using food logs.

Study procedures include a screening visit, an enrollment visit (study week 0), follow-up visits at study weeks 2, 4, 8, and 12, and a final visit at study week 18.

Screening visit: Screening procedures will occur after an overnight fast and will include a full medical history: history of diabetes care and blood sugar control; review of body weight history; review of current medications; a physical exam including height, weight, blood pressure and heart rate; a blood test to measure CBC, electrolytes, kidney function, liver function, thyroid function, cholesterol levels, hemoglobin A1C, and markers of metabolism and inflammation. We will also collect a urine sample for measurement of glucose andcreatinine. We will also measure urine glucose and creatinine levels.

Women of childbearing age will have a urine pregnancy test unless they are over age 50 and have not had a menstrual period in more than 2 years, or have had a surgical procedure which makes it impossible to become pregnant (hysterectomy). If the pregnancy test is positive, the subject will not be allowed to enroll in the study.

Enrollment visit (Study Week 0): The enrollment visit will occur after an overnight fast and will include measurement of vital signs, body composition, and resting metabolic rate. We will also distribute blood sugar logs, visual analog scales, and food logs, and we will do a 24-hour food recall assessment.

Vital signs: For all visits, vital signs will include weight (with the subject wearing a hospital gown), blood pressure lying down and standing, heart rate lying down and standing, and waist circumference.

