If the defect is combined with a serious adverse event, the study-site personnel must report the PQC to Janssen Scientific Affairs, LLC according to the serious adverse event reporting timelines. A sample of the suspected product should be maintained for further investigation if requested by Janssen Scientific Affairs, LLC.

B. Statistical Considerations

Sample Size Justification: There are no published data on change in resting metabolic rate with canagliflozin treatment. We therefore calculated sample size based on change in body weight, our primary outcome. Published data show approximately 3kg placebo-corrected weight loss after 12 weeks of treatment with canagliflozin compared to placebo in individuals with type 2 diabetes and obesity (Stenlof et al, 2013). Based on a 3 kg difference in body weight between canagliflozin and placebo and a SD of 3.3, the probability that this study will detect a treatment difference at a two-sided 0.05 significance level is 80% if we have 42 study completers. We plan to screen 60 subjects in order to enroll approximately 50 subjects (8-10 screen failures) and obtain 42 study completers (approximately 8-10 dropouts). Data from subjects who complete at least 12 weeks of treatment will be used in the final analysis.

Data analysis: Descriptive statistics with 95% confidence intervals will be used to describe baseline characteristics of the study population. The primary endpoints of change in body weight and BMI will be analyzed using an analysis of covariance (ANCOVA) model. We will use repeated measures analysis of variance to assess changes in body weight and resting metabolic rate at each study visit/timepoint. We will also analyze change in body composition between baseline and end of study. Treatment group will be the fixed effect and corresponding baseline values at the start of each treatment period will be the covariates. We will stratify based on baseline BMI, glycemic control (A1C), and diabetes treatment (lifestyle vs pharmacologic treatment at baseline). The least squares mean differences between treatments (canagliflozin vs placebo) and the associated 95% confidence intervals will be estimated based on this model.

Secondary endpoints will be analyzed using an ANCOVA model as above. The least squares mean differences between treatments and the associated 95% confidence intervals will be estimated based on this model.

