We will enroll subjects who are treated at baseline with sulfonylureas or metformin or basal insulin, but will aim to enroll a majority of subjects treated with lifestyle alone to minimize the effects of other agents on body weight. Additionally, we will only enroll subjects with stable body weight (change in body weight less than 3% for at least 3 months prior to the screening visit), which will minimize the effect of different background diabetic regimens on body weight. Subjects who drop out prior to week 8 of treatment will not be included in the final analysis.

C. Subject Selection

Inclusion criteria

- 1. Type 2 diabetes
- 2. BMI 25-45 kg/m2
- 3. Hemoglobin A1C > 6% but < 9%
- 4. Normal renal function (GFR > 60)
- 5. Age 18-75

Exclusion criteria

- 1. Type 1 diabetes
- 2. History of recurrent UTI or mycotic genital infections
- 3. Treatment with a GLP1 agent for type 2 diabetes
- 4. Pregnant or breastfeeding
- 5. 5. Individuals with A1C < 6.5% who are taking sulfonylurea or insulin

B4. POSSIBLE BENEFITS

It is not possible to say whether subjects will benefit from participation in this study.

B5. POSSIBLE RISKS AND ANALYSIS OF RISK/BENEFIT RATIO

More Common

As of 28 March 2015 approximately 12367 subjects have received canagliflozin in completed or ongoing studies of 12 weeks or longer.

• Hypoglycemia (low blood sugar) in subjects taking other medications associated with hypoglycemia. If canagliflozin is taken with another medicine that can cause low blood sugar, such as a sulfonylurea, the risk of getting low blood sugar is higher. The dose of sulfonylurea medicine may need to be lowered during the study, and study doctors will be in communication with subjects' doctors outside the study. Hypoglycemia is very common and may occur in more than 1 in 10 people on canagliflozin.

• Dizziness or lightheadedness upon standing: These symptoms may occur from a decrease in blood pressure, can occur soon after starting canagliflozin, and are more likely to occur in people on medicines to lower blood pressure including diuretics (water pills such as furosemide), on a low salt diet, older patients or those who have reduced kidney function. While you are participating in this study, you should try to avoid becoming dehydrated and you should speak to the study doctor about any changes in your diet or other medications. This side effect may occur in up to 1 in 20 people on canagliflozin, or slightly more frequently in those at risk as described above.

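### Both rules for the final analysis select randomised subjects by time on treatment, leaving the primary weight comparison open to bias of unknown size and direction

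*Combined protocol and SAP*

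**What the plan says.** Two sentences in B3, Statistical Considerations, define who is analysed. The Sample Size Justification states "Data from subjects who complete at least 12 weeks of treatment will be used in the final analysis". The last paragraph before Subject Selection states "Subjects who drop out prior to week 8 of treatment will not be included in the final analysis".

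The Data analysis paragraph gives the primary method: "The primary endpoints of change in body weight and BMI will be analyzed using an analysis of covariance (ANCOVA) model". No week is attached to weight there or in the study overview. The nearest wording on timing concerns a different endpoint: "We will also analyze change in body composition between baseline and end of study". A repeated measures analysis of variance of weight by visit is also planned, without a rule for missing values.

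The overview in B3, Study Design, schedules "follow-up visits at study weeks 2, 4, 8, and 12, and a final visit at study week 18", and "For all visits, vital signs will include weight (with the subject wearing a hospital gown"). Weight is therefore collected at every visit.

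On losses, the plan expects to "enroll approximately 50 subjects (8-10 screen failures) and obtain 42 study completers (approximately 8-10 dropouts"). Neither the timing of dropout nor its split between arms is given. No analysis of all randomised subjects is described for any endpoint.

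**The concern.** Randomisation makes the two arms comparable as randomised. Once subjects are kept or removed according to how long they stayed on treatment, the arms compared are those who stayed on canagliflozin and those who stayed on placebo. These groups may differ in ways unrelated to the drug's effect on weight. The plan itself (B5, Possible Risks) lists effects of canagliflozin that a subject could notice, such as genital yeast infection, dizziness on standing and increased urination, so different reasons for leaving in the two arms are plausible. It gives no evidence on whether leavers would have lost more or less weight than stayers.

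At stake is the primary result of a small double-blind trial. The restriction also discards primary-endpoint data already in hand, namely the early weights of the excluded subjects.

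**Working it through.** **1. The plan's own figure.** Inputs from the Sample Size Justification: difference 3 kg, SD 3.3 kg, two-sided 0.05, power 80%, 42 completers. A two-sample t-test has power 0.79997 with 20 per arm and 0.820 with 21 per arm, so 21 per arm (42 in total) is the smallest equal-arm size that reaches 80%. The figure reproduces. The standard error of the difference at that size is 3.3 × √(2/21) = 1.02 kg.

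**2. The two rules side by side.**

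| Subject leaves | 12-week rule | 8-week rule | Scheduled weights already taken after baseline |
|---|---|---|---|
| before week 2 | out | out | none |
| weeks 2-4 | out | out | week 2 |
| weeks 4-8 | out | out | weeks 2, 4 |
| weeks 8-12 | out | not excluded | weeks 2, 4, 8 |
| weeks 12-18 | in | in | weeks 2, 4, 8, 12; none at week 18 |

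Each rule sorts subjects by time on treatment. They differ only for weeks 8-12.

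**3. When the restriction biases the difference.** In one arm, let f be the fraction excluded and k the gap: mean weight change of the excluded minus that of the retained, positive if the excluded would have lost less. Since the mean of all = mean of retained + f × k, the retained mean is off by −f × k. For canagliflozin (c) minus placebo (p):

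bias = −(f_c × k_c − f_p × k_p)

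This is zero whenever the two products are equal. That covers similar dropout with similar gaps, and also any dropout imbalance when k = 0 in both arms.

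**4. How many are affected (assumed even dropout over 18 weeks, 8-10 of 50, 25 per arm).**
- Excluded by the 12-week rule: 12/18 × 8 to 12/18 × 10 = 5.3-6.7 subjects (11-13%).
- Excluded by the 8-week rule: 8/18 × 8 to 8/18 × 10 = 3.6-4.4 (7-9%).
- Status depends on the rule (weeks 8-12): 4/18 × 8 to 4/18 × 10 = 1.8-2.2.
- Kept without a week-18 weight (weeks 12-18): 6/18 × 8 to 6/18 × 10 = 2.7-3.3.
- Weights unused under the 12-week rule: (2×0 + 2×1 + 4×2 + 4×3)/12 = 22/12 = 1.83 per excluded subject, or 9.8-12.2 in total.

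The overview speaks of 42 randomised, not about 50. The excluded fractions, and so the kilograms below, do not change if the same 16-20% leave.

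**5. Illustrative bias (gaps of 1-3 kg are assumed).**
- 12-week rule, equal dropout, gap in one arm only: 5.33/50 × 1 = 0.11 to 6.67/50 × 3 = 0.40 kg. The effect is overstated if that arm is canagliflozin and understated if it is placebo.
- 8-week rule, same assumptions: 3.56/50 × 1 = 0.07 to 4.44/50 × 3 = 0.27 kg.
- 12-week rule, all dropouts in one arm: 5.33/25 × 1 = 0.21 to 6.67/25 × 3 = 0.80 kg.
- Eight excluded with the same gap in both arms: split 4/4 gives 0; split 6/2 gives (6/25 − 2/25) × 1 to × 3 = 0.16-0.48 kg, with the sign depending on which arm loses six.

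The main illustration of 0.11-0.40 kg is 0.11/1.02 to 0.40/1.02, about 0.1-0.4 of a standard error.

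**The case against.** Several stronger readings are tempting, and the documents do not support them.

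- *The two cut-offs contradict each other.* They need not. Anyone leaving before week 8 fails both rules, and applied together they amount to a single 12-week rule. What remains unclear is the status of about two subjects who leave in weeks 8-12.
- *The primary endpoint has no time point.* Treatment lasts 18 weeks and the final visit is at week 18, so week 18 is the natural reading, although it is not written for weight and the 3 kg planning figure is a 12-week one. This calls for a clarification.
- *Week 12-18 leavers have no rule.* They do have an inclusion rule. Only the choice of weight for them is missing, and on the even-dropout assumption that concerns about three subjects.
- *The result will favour canagliflozin, or any dropout imbalance biases it.* The formula shows neither follows. The bias may go either way or be zero.

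A fair critic would add that every kilogram figure is assumed and that most are well below the standard error. The even spread is also open to dispute. If a completer is someone with at least 12 weeks, all 8-10 dropouts fall before week 12, and the one-arm illustration becomes 8/50 × 1 = 0.16 to 10/50 × 3 = 0.60 kg. That enlarges the exclusion, but mainly it confirms that the size cannot be derived from the documents.

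All of this stands as a limit on the claim. The core is not answered: the stated rules select after randomisation, and nothing in the plan analyses everyone randomised.

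**Conclusion.** The concern holds on principle. A stated rule, not a missing detail, removes randomised subjects from the primary comparison according to time on treatment, whichever cut-off governs. It also leaves their early weights unused. This should be corrected before unblinding.

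The size and direction of any bias are unknown. The 0.11-0.40 kg illustration rests on 8-10 dropouts among about 50, even timing, equal dropout in the arms and a 1-3 kg gap in one arm only. It should be read beside a standard error of about 1.0 kg, not as a forecast. The sample-size arithmetic is sound. The status of week 8-12 leavers and the unstated week for weight are clarifications only.

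**What to change.** - **Population.** Replace both duration rules, as the definition of the primary population, with all randomised subjects in their assigned arm.
- **Time point.** Name week 18 as the primary time point for weight and BMI.
- **Method.** Keep the planned ANCOVA. Multiply impute missing week-18 values, by arm, from baseline and all earlier visits.
- **Interpretation.** State that this treats leavers as following similar subjects who stayed, since the plan describes no weights after a subject leaves.
- **Sensitivity analysis.** Keep one duration-based set with a single cut-off, and state which weight represents week 12-18 leavers. This also settles the week 8-12 question. A delta-adjusted analysis, for dropout that depends on unobserved weight, is optional.

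The cost is a few sentences of analysis text, slightly more analysis work and possibly a less favourable estimate. Weight is already scheduled at every visit, so no visit is added. If about 50 are randomised, t-test power for 3 kg lies between 0.800 (as if only 40 contributed) and 0.883 (as if all 50 had a week-18 weight). A lower power of 0.71-0.75 would apply only if dropouts on canagliflozin were counted as keeping no benefit, which dilutes the effect to 3 × 0.80 = 2.40 or 3 × 0.84 = 2.52 kg. That is a different effect from the one proposed here.
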